### **7.4 Assessment of locoregional recurrence 24 months after registration**

Two years after the full course of radiochemotherapy the patient will be assessed by the radiation oncologist and gynecologic oncologist. A photograph of the local situation at the vulva area with an adjacent ruler must be taken. Measurements should be done according to RECIST criteria (Addendum 2). Whether or not reconstructive surgery or exenterative surgery with stoma formation has been performed should be mentioned. Morbidity should be described such as lymphedema, fibrosis, and continence (both urinary and fecal).

## 7.5 Overall survival

Overall survival is the time from registration of the patient in the trial until date of death due to any cause. Patients still alive at time of analysis will be censored at the date she was last known to be alive. Date of death should be reported on the follow-up forms.

## 8. Statistical considerations

### Statistical and Analytical Plan

This is a phase II study to investigate the efficacy of definitive radiochemotherapy in patients with locally advanced vulva carcinoma. In order to minimize the expected number of patients treated in the event that the regimen proves to be very disappointing, a two-stage design will be used for patient accrual [41].

Primary endpoint of this study is percentage of patients obtaining an objective complete (locoregional) remission according to RECIST criteria [42] at 12 weeks after the end of the radiochemotherapy.

Although the radiochemotherapy combination will result in fewer stoma formations it will not be of much interest if the complete response rate is less than 35%. In that case 65% or more patients need salvage surgery with an unacceptable increase in morbidity. However, a response rate of 50% or more will be considered interesting enough to warrant further research because it approaches the local control rate of extensive surgery except for the price of 100% stoma formation. With  $\alpha$  set at 0.05 and  $\beta$  at 0.2 the minimax design suggests 42 patients for the first stage. If less than 14 responses are observed among the first 42 patients then the trial will be terminated. Otherwise the trial will continue to accrue up to 68 patients. A total of at least 30 responses would then be required in order to claim activity under these predefined constraints.

It is expected that the participating institutes will be able to accrue approximately 20-30 patients per year. Therefore, the estimated total accrual time will be about three years.

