### **4. Trial design**

The trial is a non-randomized multi-centre phase II study. The primary endpoint is the locoregional control rate defined as clinically or pathologically proven absence of tumor in the vulvar and groin area 12 weeks after the last dosis of radiochemotherapy and after groin dissection in cN1,2 patients. The optimal two-stage design [59] is proposed in order to minimize the sample size if the treatment has low activity defined as poor locoregional control.

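### The stage-1 stopping limit in Section 8 is one response too lenient for the two-stage design its numbers describe, and Section 4 gives that design a different name

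*Protocol*

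**What the plan says.** Section 4 (Trial design) gives no numbers. It states: "The optimal two-stage design [59] is proposed in order to minimize the sample size if the treatment has low activity".

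Section 8 (Statistical and Analytical Plan) explains the two-stage approach with the words "In order to minimize the expected number of patients treated in the event that the regimen proves to be very disappointing". It then fixes these inputs:

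- Uninteresting rate: "it will not be of much interest if the complete response rate is less than 35" percent.
- Rate of interest: "a response rate of 50% or more will be considered interesting enough to warrant further research".
- Alpha is 0.05, and with beta "at 0.2 the minimax design suggests 42 patients for the first stage".
- Interim rule: "If less than 14 responses are observed among the first 42 patients then the trial will be terminated".
- Continuation: "Otherwise the trial will continue to accrue up to 68 patients".
- Final rule: activity is claimed with at least 30 responses.

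The protocol states no probability of early stopping and no expected sample size.

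**The concern.** Simon two-stage designs are usually printed as r1/n1 and r/n, where r1 and r are rejection limits: stop if responses are r1 or fewer, and reject the regimen if total responses are r or fewer. A limit of 14 therefore means stopping at 14 or fewer. Section 8 stops only below 14. If 14 is the rejection limit of the intended design, the interim rule misstates it by one response.

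What is at stake is how often an inadequate regimen is stopped after 42 patients. Section 8 itself says that below a 35% complete response rate, 65% or more of the patients would need salvage surgery, with an unacceptable increase in morbidity. Each trial that continues wrongly enrols up to 68 − 42 = 26 more patients.

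Section 4 calls the design optimal and Section 8 calls it minimax. These are different criteria, so the label cannot tell a reader which limits were meant.

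**Working it through.** **Inputs, all from Section 8.** p0 = 0.35, p1 = 0.50, alpha 0.05, beta 0.2 (power 0.80), n1 = 42, n = 68, printed limits 14 and 30.

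**Formulas.** Let X1 ~ Bin(42, p) and X2 ~ Bin(26, p), independent, with stage-1 limit r1 and final limit r.

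- Probability of early stopping: PET(p) = P(X1 ≤ r1).
- Expected sample size: E[N] = 42 + 26 × (1 − PET).
- Probability of claiming activity: sum over x > r1 of P(X1 = x) × P(X2 > r − x). At p0 this is alpha; at p1 it is power.

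**Step 1. Do the stated rules give the stated error rates?**

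| Stage 1 | Final | alpha | power |
|---|---|---|---|
| stop ≤13 (as written) | claim ≥30 (as written) | 0.0750 | 0.862 |
| stop ≤14 | claim ≥30 | 0.0744 | 0.860 |
| stop ≤13 | claim ≥31 | 0.0460 | 0.8017 |
| stop ≤14 | claim ≥31 | 0.0458 | 0.8007 |

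As written, alpha is 0.075 rather than 0.05. Moving the stage-1 limit alone leaves it at 0.0744. Moving the final cutoff to 31 brings it below 0.05 with either stage-1 limit.

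**Step 2. Which design do the numbers belong to?** An exhaustive search over two-stage designs with alpha ≤ 0.05 and power ≥ 0.80 shows that, at n = 68, the one with the smallest E[N] at 35% is r1/n1 = 14/42, r/n = 30/68. Its alpha is 0.0458, power 0.8007, PET 0.4808 and E[N] 55.5. All four printed numbers coincide with it when 14 and 30 are read as rejection limits. At n1 = 42, 14 is also the largest r1 that keeps the power: r1 = 15 gives 0.797.

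**Step 3. What does the stage-1 slip do?** The two limits differ only at the outcome 14/42 = 33.3%. At p = 0.35 that outcome has probability 0.4808 − 0.3544 = 0.1264.

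- As written at 35%: E[N] = 42 + 26 × (1 − 0.3544) = 58.8.
- Corrected at 35%: E[N] = 42 + 26 × (1 − 0.4808) = 55.5.

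| True rate | PET as written | PET corrected | E[N] as written | E[N] corrected |
|---|---|---|---|---|
| 20% | 97.0% | 98.7% | 42.8 | 42.3 |
| 25% | 85.7% | 92.0% | 45.7 | 44.1 |
| 30% | 62.7% | 74.3% | 51.7 | 48.7 |
| 35% | 35.4% | 48.1% | 58.8 | 55.5 |

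**Step 4. Cost in power.** With the final cutoff at ≥31: 0.8017 − 0.8007 = 0.0010, or 0.1 percentage point. With the written ≥30: 0.8619 − 0.8599 = 0.0020, or 0.2 points.

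**Step 5. The label.** For these inputs the strict minimax design has n = 66 (22/55, 29/66; alpha 0.0499, power 0.8005). The design with the smallest E[N] at 35% overall, the optimal one, is 10/27, 33/77 (PET 0.670, E[N] 43.5). So 42/68 is neither strictly minimax nor optimal.

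**The case against.** **The interim rule breaks no stated constraint.** This stands. The protocol promises no stopping probability or expected sample size, and stopping at 13 or fewer meets alpha and power once the final cutoff is 31. The case rests on the match of all four numbers to one design and on the final cutoff showing the same one-response shift, not on a violated error rate.

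**The effect is small for the scenario the protocol names.** This also stands. Section 8 speaks of a very disappointing regimen, not one exactly at 35%. At a true 25% the slip costs 45.7 − 44.1 = 1.6 expected patients, and at 20% about 0.4. At 35% it costs 3.3.

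**Optimal may be loose wording.** It may echo the title of the two-stage paper in the reference list, and Section 8 names minimax and carries all the operative numbers, so conduct is not ambiguous. That is fair. What remains is that the two sections use different names and that neither name identifies 42/68 exactly.

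A reader might go further and infer that the protocol committed itself to the optimal design, so that early stopping is about half as likely as intended (35% against 67%) and the trial should move to 10/27, 33/77. The documents do not support this. Most of that gap comes from the choice of design family, not from the slip. The stated aim can be read as a reason for any two-stage futility design. The switch would also raise the maximum from 68 to 77 patients, with expected accrual of 20 to 30 a year.

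**Conclusion.** The stage-1 limit is very probably a transcription slip: a rejection limit of 14 was written as stopping below 14. It weakens early stopping by 48.1 − 35.4 = 12.7 percentage points at a true rate of 35% and by 92.0 − 85.7 = 6.3 points at 25%. The cost is 3.3 and 1.6 expected patients respectively.

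It is tempting to blame this limit for the failure to hold alpha at 0.05. That is not so: the excess comes from the final cutoff of 30.

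The conclusion assumes independent binary responses, Simon's one-sided convention for alpha, and that 14/42, 30/68 was the intended design. The protocol does not print it in that notation. The point is worth correcting because the rule is binding and the correction is nearly free; it does not overturn the design.

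**What to change.** 1. In Section 8, state that accrual ends if 14 or fewer of the first 42 patients respond.
2. In the same change, require at least 31 responses among 68 to claim activity. Together these give alpha 0.046 and power 0.801. The stage-1 change alone would leave alpha at 0.074.
3. In Sections 4 and 8, describe one design by its limits, r1/n1 = 14/42 and r/n = 30/68, and define them as rejection limits. Add its properties: probability of stopping at a true 35% of 48%, and expected sample size 55.5. Do not rely on the label optimal or minimax alone.

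This is a change of wording in two sections. The maximum stays at 68. With the final cutoff at 31, the stage-1 correction costs 0.1 percentage point of power.

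### The final success cutoff of at least 30 responses in 68 patients gives a type I error of 7.5%, not the stated 5%; 31 are needed

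*Protocol*

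**What the plan says.** The rule and its error rates stand together in the protocol, section 8, under Statistical and Analytical Plan.

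- Uninteresting rate: the combination would be of little value, as "it will not be of much interest if the complete response rate is less than 35"%.
- Rate of interest: "a response rate of 50% or more will be considered interesting enough to warrant further research".
- Error rates: alpha 0.05 and beta 0.2, for which "the minimax design suggests 42 patients for the first stage".
- First stage: "If less than 14 responses are observed among the first 42 patients then the trial will be terminated".
- Second stage: "Otherwise the trial will continue to accrue up to 68 patients".
- Final decision: "A total of at least 30 responses would then be required in order to claim activity under these predefined constraints".

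The last sentence ties the cutoff of 30 to the stated alpha and beta. Section 4 (Trial design) also names a two-stage design but gives no cutoffs or error rates. No other section gives a different cutoff or a larger alpha.

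**The concern.** A two-stage design is usually tabulated by its rejection bounds: r1 and r are the largest numbers of responses at which the regimen is still judged inactive. Success then requires more than r. If r is copied as the minimum for success, the cutoff is one too low and the type I error exceeds its limit. The combination of 30 in 68 with alpha 0.05 and power of 80% suggested that this had happened.

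The cutoff decides whether the regimen is called active in a single-arm trial with no comparator to fall back on. The protocol's own reason for the 35% limit is that at such a rate 65% or more of patients would need salvage surgery, with more morbidity than is acceptable. A larger chance of calling such a regimen active is therefore not a formality.

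**Working it through.** **Inputs**, all from protocol section 8: p0 = 0.35, p1 = 0.50, alpha = 0.05, beta = 0.2 (power 0.80), n1 = 42, n = 68, hence 68 − 42 = 26 patients in the second stage. The trial continues at 14 or more responses in 42 and claims activity at 30 or more in 68. Sidedness is not stated; the rule itself uses the upper tail only.

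**Formula.** With first-stage cutoff c1 (continue if X1 ≥ c1) and final cutoff c (claim if the total is ≥ c),

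P(claim | p) = Σ over x from c1 to 42 of P[Bin(42, p) = x] × P[Bin(26, p) ≥ c − x].

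This is the type I error at p = 0.35 and the power at p = 0.50.

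**Step 1: the rule as written, and its variants.**

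| Continue if | Claim if | Alpha (p = 0.35) | Power (p = 0.50) |
|---|---|---|---|
| ≥ 14/42 (as written) | ≥ 30/68 (as written) | 0.0750 | 0.862 |
| ≥ 15/42 | ≥ 30/68 | 0.0744 | 0.860 |
| no interim look | ≥ 30/68 | 0.0752 | 0.8625 |
| ≥ 14/42 | ≥ 31/68 | 0.0460 | 0.8017 |
| ≥ 15/42 | ≥ 31/68 | 0.0458 | 0.8007 |

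The stated alpha of 0.05 is not reproduced with a cutoff of 30. The excess is 0.0750 / 0.05 = 1.5 times. Power of 0.862 does not match the planned 0.80 either, whereas a cutoff of 31 meets both targets.

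**Step 2: where the numbers come from.** An exhaustive search over two-stage designs with alpha ≤ 0.05 and power ≥ 0.80, in which the regimen is rejected at r1 or fewer responses in n1 and at r or fewer in n, was run. At n = 68, the design with the lowest expected sample size under p0 is r1/n1 = 14/42 and r/n = 30/68, with alpha 0.0458 and power 0.8007. These are the protocol's four numbers. In that solution 14 responses in 42 stop the trial and 30 in 68 are a failure. The protocol has 14 continuing and 30 succeeding, so both boundaries are one too low.

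**Step 3: can another first-stage rule save a cutoff of 30?** Stopping early for futility can only lower alpha, so every first-stage cutoff at 42 patients was tried with ≥ 30/68 kept:

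- continue at ≥ 18: alpha 0.0602, power 0.804;
- continue at ≥ 19: alpha 0.0487, power 0.746.

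Alpha first falls below 0.05 at ≥ 19, where power is already below 0.80. No first-stage cutoff meets both constraints.

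**Step 4: the first-stage boundary.** Its effect on alpha is small (0.0750 against 0.0744). Its effect on early stopping is larger. At p0 the chance of stopping is 35.4% when 13 or fewer responses stop the trial, and 48.1% when 14 or fewer do. The expected sample size is 42 + 26 × (1 − 0.354) = 58.8 in the first case and 42 + 26 × (1 − 0.481) = 55.5 in the second.

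**The case against.** The strongest reply concerns consequence. The rule as written and the corrected final cutoff disagree only when exactly 30 of 68 patients respond after the trial has continued. That has probability 0.0750 − 0.0460 = 2.9% at a true rate of 35% and 0.862 − 0.802 = 6.0% at 50%. A positive result only has to justify further research, and section 2.1 also names gaining experience as part of the primary objective. This limits the practical harm, and it stands. It does not make the stated alpha true, and the correction needs no extra patients.

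A second reply is that a strict first-stage rule could bring alpha under 0.05 with 30 kept. It could, at 19 or more in 42, but power is then 74.6%, and that is not the rule in the protocol.

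A third is that the account of how the slip arose is inference, since the cited design paper is not at hand. That is fair. The match with the search makes a misread bound likely, but the 7.5% follows from the rule as worded and needs no account of its origin.

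Reading alpha as two-sided would only widen the gap. A separate analysis plan could not resolve the matter either, because the cutoff and the error rate contradict each other within one paragraph of the protocol.

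**Conclusion.** The concern holds. The decision rule in section 8 has an exact type I error of 7.5% at a true complete response rate of 35%, against the stated 5%, with power of 86.2% at 50%. The cutoff consistent with the stated constraints is at least 31 of 68, with alpha 0.046 and power 0.80 whichever first-stage boundary is used. The result assumes that the primary endpoint is a simple responder count with independent patients, that exactly 42 and 68 patients are counted, and that 35% is the null rate. Since that is the upper edge of the uninteresting range, 7.5% is the worst case over the range, which is the usual meaning of alpha.

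The first-stage boundary appears to carry the same shift. That matters little for alpha but raises the expected sample size under p0 from 55.5 to 58.8, which works against the protocol's stated reason for using two stages.

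**What to change.** In section 8, require at least 31 responses (more than 30) among 68 patients to claim activity, and state the exact properties of the rule. This is the essential change.

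In the same edit, settle the first-stage boundary and report the figures that go with it:

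- stop at 14 or fewer of 42, as in the design that the search returns: alpha 0.0458, power 0.8007, expected sample size 55.5 at p0;
- keep stopping at 13 or fewer of 42: alpha 0.0460, power 0.8017, expected sample size 58.8 at p0.

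The cost is one or two numbers and a sentence. No patients are added and the sample sizes stay at 42 and 68. Power falls from the unplanned 86% to the planned 80%. The change should be made and dated before the response results are known, so that it cannot be read as a reaction to the data.

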### Statistical analysis

All patients that started the primary radiochemotherapy will be considered in the analysis of locoregional response and toxicity. Subjects will be designated as responders and non-responders at week 12 after the end of radiochemotherapy.

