### **2.2 secondary objectives**

The secondary objective would be to determine short-term morbidity defined as desquamation of the skin, infection, long-term morbidity defined as edema, fibrosis, the incidence of fecal and or urinary continence, and or incidence of reconstructive surgery performed and treatment related mortality. Longterm morbidity and the rate of locoregional recurrences will be evaluated at 24 months after the end of radiochemotherapy.

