### *5.3.2 treatment for the regional lymph nodes*

Patients with cN0 groin lymph nodes and no enlarged/suspicious lymph nodes on imaging (ultrasound/CT/MRI) will be treated with radiochemotherapy only. Patients with cN1/2 groin lymph nodes are treated with either a nodal debulking upfront or a bilateral inguino-femoral lymph node dissection 8-12 weeks after the radiotherapy. It is recommended, in case of residual vulvar disease, to combine local and regional surgical treatment.

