## 6.6 Summary Table

Required investigations	Prestudy	After initial surgery*	During radiochemotherapy	After radiochemotherapy	After secondary surgery**	During follow up
						yr. 1-2: 3-monthly yr 2-5: 6-monthly
Day	-28 tot 0	-28 tot 0	Start day 0  weekly	4, 8 and 12 weeks after last radiochemotherapy	> 12 weeks after last radiochemotherapy	
History	X 1					
Phys/gyn exam	X 1/ 2			X 1/2		X 1/2
WHO	X 1		X 2/ 3	X 2		
TNM	X 1					
Photo	X 1			X 2		
Chest X-ray	X 1					
CT/MRI/US	X 1			X 1/2 ***		
Haematology	X 1		X 2/ 3	X 1		
Biochemistry	X 1		X 2/ 3	X 1		
Path lymph nodes		X 1			X 1	
Path primary tumor	X 1				X 1	
Short-term morb		X 1	X 2/ 3	X 2	X 1	
Long term morb						X 1/2

\* Only when upfront surgery is performed for clinically (and pathologically confirmed) positive groin lymph node metastases

\*\* Only when salvage surgery for the primary or groin dissection is performed

\*\*\* Optional

- 1) gynecologic oncologist
- 2) radiation oncologist
- 3) medical oncologist

 Haematology: Hb, Ht, platelets, leucocytes  
Chemistry: Na, K, Creatinin, ureum, Bilirubin, gGT, AF, ASAT, ALAT, LDH.  
Creatinin clearance if plasma creatinin > 100 umol/l.

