### **7.2 Short-term morbidity**

This is defined as any treatment related morbidity until the end of radiotherapy or discharge from the hospital. Any toxicity/morbidity should be reported according to the CTC guidelines version 3 (addendum 2). Most common complications are: skin toxicity, infections, gastrointestinal toxicity, and urinary toxicity. Surgical morbidity can consist of excessive blood loss during surgery (>500ml), damage/laceration to femoral vein, artery or nerve or wound breakdown after surgery and/or severe infections (sepsis).

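### The toxicity population requires that radiochemotherapy was started, so a registered patient whose upfront groin debulking prevents that start falls outside the morbidity and treatment-related mortality rates

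*Protocol*

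**What the plan says.** The protocol sets the population in section 8, under Statistical analysis: "All patients that started the primary radiochemotherapy will be considered in the analysis of locoregional response and toxicity". This is the only place that names a set for toxicity.

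Four other places describe treatment and events that can come before radiochemotherapy:

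- **5.3.2:** patients with cN1/2 groins "are treated with either a nodal debulking upfront or a bilateral inguino-femoral lymph node dissection", the latter 8-12 weeks after radiotherapy.
- **6.6:** the schedule has a column for the period after initial surgery, at day -28 to 0, in which short-term morbidity is marked for recording. Its footnote reads: "Only when upfront surgery is performed for clinically (and pathologically confirmed) positive groin lymph node metastases".
- **7.2:** on short-term morbidity, "This is defined as any treatment related morbidity until the end of radiotherapy or discharge from the hospital". Surgical events are included: "Surgical morbidity can consist of excessive blood loss during surgery (>500ml), damage/laceration to femoral vein, artery or nerve or wound breakdown after surgery". Severe infection (sepsis) is named as well.
- **2.2:** the secondary objectives include "incidence of reconstructive surgery performed and treatment related mortality". Section 2.3 lists morbidity and treatment-related toxicity as a secondary endpoint.

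Two further statements concern populations. Section 5.5, on stopping protocol treatment, says that patients are evaluated by intention to treat. Section 7 includes all eligible patients, but for the response rate only.

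**The concern.** The protocol offers a surgical treatment before radiochemotherapy, schedules the recording of its complications and defines them as morbidity. It then ties the toxicity analysis to a later event, the start of radiochemotherapy. A serious complication of the surgery can prevent that event. The patient is then excluded because of the outcome that the analysis is meant to measure.

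At stake is the accuracy of two descriptive secondary results, short-term morbidity and treatment-related mortality. In a trial of at most 68 patients, a mortality rate rests on very few events, so a single omitted death is visible. The primary response analysis is not the subject of this point.

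**Working it through.** The protocol gives no figure for this point, so there is none to reproduce. The check is a comparison of passages, followed by an illustration.

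**Step 1: can a patient fall outside the set?** Take a registered cN1/2 patient who has upfront debulking.

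- Her short-term morbidity is recorded after surgery, before radiochemotherapy (6.6).
- Wound breakdown, vessel injury or sepsis counts as short-term morbidity (7.2).
- If the complication prevents radiochemotherapy, she has not started it and is not in the set named in section 8.

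On the other route, dissection after radiotherapy, the patient has already started. Her surgical complications therefore always fall inside the set.

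**Step 2: does another passage bring her back?**

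- Section 5.5 (intention to treat) appears among the rules for discontinuation and names no toxicity set. If it applies generally, it conflicts with section 8.
- Section 7 (all eligible patients) covers response only.
- The Safety Monitoring text in section 8 and section 12.2 govern monitoring and reporting. They define no analysis population.
- Section 7.5 counts a death from registration onwards, but in overall survival, not in treatment-related mortality.

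None of these supplies a wider toxicity set.

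**Step 3: direction.** Let N be the registered patients (all assumed to receive some protocol treatment), d those with a debulking event who therefore never start, and e the events among starters. Then:

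- starters only: e/(N − d)
- all treated: (e + d)/N
- difference: (e + d)/N − e/(N − d) = d(N − d − e)/[N(N − d)], which is never negative.

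An exclusion caused by the event can therefore only lower the rate, or leave it unchanged if every starter also had an event.

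**Step 4: illustration for treatment-related mortality.** N = 68 is the maximum sample in section 8. The values of d and e are assumed, because the protocol gives neither the number debulked nor any debulking risk.

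| d | e | Starters only | All treated | Difference |
|---|---|---|---|---|
| 1 | 0 | 0/67 = 0% | 1/68 = 1.5% | 1.5 points |
| 1 | 1 | 1/67 = 1.5% | 2/68 = 2.9% | 1.4 points |
| 2 | 1 | 1/66 = 1.5% | 3/68 = 4.4% | 2.9 points |

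**Step 5: how likely is at least one such patient?** With m patients debulked upfront and risk q each, the chance is 1 − (1 − q)^m. Both inputs are assumed:

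- m = 10, q = 1%: 1 − 0.99^10 = 9.6%
- m = 20, q = 3%: 1 − 0.97^20 = 45.6%
- m = 30, q = 5%: 1 − 0.95^30 = 78.5%

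The range is too wide to support any single estimate.

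**The case against.** **Registration may come after debulking.** Section 6 has protocol treatment start within four weeks of registration, and section 10 requires registration before treatment. Neither says whether debulking counts as that treatment. In 6.6 the column after initial surgery shares its day range with the prestudy column. If debulking can come first, the patient may never enter the trial, and a set of registered patients would not capture her either. This stands as a limit on the point, and the fix must settle it.

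**The sentence does not say that only starters count, and it names toxicity rather than surgical morbidity or mortality.** Section 2.3 lists morbidity and toxicity side by side. However, 7.2 treats the two terms together, and no other population is given. The restrictive reading is the natural one, though not the only one.

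**The event is not lost.** A reader might infer that it disappears from the trial. The documents do not support that. Adverse events are monitored and reported semi-annually, serious events during the treatment period must be reported, and a registered patient's death counts in overall survival. What is missing is her place in the planned rates.

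**A set of patients who started treatment is conventional for a radiochemotherapy trial.** This is right for radiochemotherapy toxicity, and the fix keeps it. It does not suit complications of surgery given beforehand.

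**This is detail for a statistical analysis plan.** That would hold if the protocol had left the population open. It names one, and a plan that follows it inherits the gap.

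**Conclusion.** The point holds in a limited form. Section 8 conditions the toxicity analysis on having started radiochemotherapy, while 5.3.2, 6.6 and 7.2 create recorded, countable morbidity before that start. A registered patient kept from radiochemotherapy by a debulking event is outside the set, and this biases the morbidity and treatment-related mortality rates downwards.

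The conclusion rests on two readings: that registration precedes debulking, and that the section 8 sentence also governs surgical morbidity and mortality. Neither is stated outright.

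The size cannot be derived. One such death means 1/68 = 1.5% against 0/67. A reader might try to go further from the 50-60% rate of positive nodes in section 1.1 to a number of lost patients, or to a percentage understatement for the upfront route. The documents do not support this. That rate covers all positive nodes and not only cN1/2, and neither the share debulked upfront nor the proportion who fail to start is given. A reader might also infer a biased comparison between the two groin routes, but the single-arm trial plans none. The affected results are descriptive and carry no test or decision rule.

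**What to change.** In section 8, under Statistical analysis, separate the response set from the safety set. Suggested safety wording:

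*Radiochemotherapy toxicity is analysed in patients who started radiochemotherapy. Surgical morbidity and treatment-related mortality are analysed in all registered patients who received any protocol treatment, including upfront nodal debulking.*

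Two clarifications belong with it:

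- State that registration precedes upfront debulking or, if it may not, that such surgery is outside the safety set.
- Reconcile section 8 with the intention-to-treat sentence in 5.5, so that one rule applies to each analysis.

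The cost is a few sentences. Section 6.6 already schedules the morbidity record after initial surgery, and neither the sample size nor any treatment rule changes. The downside is that reported morbidity may be slightly higher.
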